#### 6.4.8.4 Evaluating Adverse Events

An investigator who is a qualified physician will evaluate all adverse events according to the NCI Common Terminology for Adverse Events (CTCAE), version 4.0. Any adverse event which changes CTCAE grade over the course of a given episode will have each change of grade recorded on the adverse event case report forms/worksheets.

All adverse events regardless of CTCAE grade must also be evaluated for seriousness.

Table 6 Evaluating Adverse Events

An investigator, who is a qualified physician, will evaluate all adverse events as to:

V4.0 CTCAE Grading	Grade 1	Mild; asymptomatic or mild symptoms; clinical or diagnostic observations only; intervention not indicated.
	Grade 2	Moderate; minimal, local or noninvasive intervention indicated; limiting age-appropriate instrumental ADL.
	Grade 3	Severe or medically significant but not immediately life-threatening; hospitalization or prolongation of hospitalization indicated; disabling; limiting self-care ADL.
	Grade 4	Life threatening consequences; urgent intervention indicated.
	Grade 5	Death related to AE
Seriousness	A serious adverse event is any adverse event occurring at any dose or during any use of Merck product that:	
	† Results in death ; or	
	† Is life threatening ; or places the subject, in the view of the investigator, at immediate risk of death from the event as it occurred (Note: This does not include an adverse event that, had it occurred in a more severe form, might have caused death.); or	
	† Results in a persistent or significant disability/incapacity (substantial disruption of one's ability to conduct normal life functions); or	
	† Results in or prolongs an existing inpatient hospitalization (hospitalization is defined as an inpatient admission, regardless of length of stay, even if the hospitalization is a precautionary measure for continued observation. (Note: Hospitalization for an elective procedure to treat a pre-existing condition that has not worsened is not a serious adverse event. A pre-existing condition is a clinical condition that is diagnosed prior to the use of a Merck product and is documented in the patient's medical history.); or	
	† Is a congenital anomaly/birth defect (in offspring of subject taking the product regardless of time to diagnosis); or	
	Is a new cancer (that is not a condition of the study) (although not serious per ICH definition, is reportable to the Principal Investigator within 24 hours and to Merck within 2 working days to meet certain local requirements); or	
	Is an overdose (whether accidental or intentional). Any adverse event associated with an overdose is considered a serious adverse event for collection purposes. An overdose that is not associated with an adverse event is considered a non-serious event of clinical interest and must be reported within 24 hours to the Principal Investigator and to Merck within 2 working days.	
	Other important medical events that may not result in death, not be life threatening, or not require hospitalization may be considered a serious adverse event when, based upon appropriate medical judgment, the event may jeopardize the subject and may require medical or surgical intervention to prevent one of the outcomes listed previously (designated above by a †).	
Duration	Record the start and stop dates of the adverse event. If less than 1 day, indicate the appropriate length of time and units	
Action taken	Did the adverse event cause Merck product to be discontinued?	

Relationship to Merck Product	Did Merck product cause the adverse event? The determination of the likelihood that Merck product caused the adverse event will be provided by an investigator who is a qualified physician. The investigator's signed/dated initials on the source document or worksheet that supports the causality noted on the AE form, ensures that a medically qualified assessment of causality was done. This initialed document must be retained for the required regulatory time frame. The criteria below are intended as reference guidelines to assist the investigator in assessing the likelihood of a relationship between the test drug and the adverse event based upon the available information. The following components are to be used to assess the relationship between Merck product and the AE; the greater the correlation with the components and their respective elements (in number and/or intensity), the more likely Merck product caused the adverse event (AE):
Exposure	Is there evidence that the subject was actually exposed to Merck product such as: reliable history, acceptable compliance assessment (pill count, diary, etc.), expected pharmacologic effect, or measurement of drug/metabolite in bodily specimen?
Time Course	Did the AE follow in a reasonable temporal sequence from administration of Merck product? Is the time of onset of the AE compatible with a drug-induced effect (applies to trials with investigational medicinal product)?
Likely Cause	Is the AE not reasonably explained by another etiology such as underlying disease, other drug(s)/vaccine(s), or other host or environmental factors

Relationship	The following components are to be used to assess the relationship between the test drug and the AE: (continued)	
to Merck Product (continued)	Dechallenge	Was Merck product discontinued or dose/exposure/frequency reduced?  If yes, did the AE resolve or improve?  If yes, this is a positive dechallenge. If no, this is a negative dechallenge.  (Note: This criterion is not applicable if: (1) the AE resulted in death or permanent disability; (2) the AE resolved/improved despite continuation of the product; or (3) the trial is a single-dose drug trial); or (4) product(s) is/are only used one time.)
	Rechallenge	Was the subject re-exposed to Merck product in this study?  If yes, did the AE recur or worsen?  If yes, this is a positive rechallenge. If no, this is a negative rechallenge.  (Note: This criterion is not applicable if: (1) the initial AE resulted in death or permanent disability, or (2) the trial is a single-dose drug trial); or (3) product(s) is/are used only one time).  NOTE: IF A RECHALLENGE IS PLANNED FOR AN ADVERSE EVENT WHICH WAS SERIOUS AND WHICH MAY HAVE BEEN CAUSED BY MERCK PRODUCT, OR IF REEXPOSURE TO MERCK PRODUCT POSES ADDITIONAL POTENTIAL SIGNIFICANT RISK TO THE SUBJECT, THEN THE RECHALLENGE MUST BE APPROVED IN ADVANCE BY THE PRINCIPAL INVESTIGATOR AS PER DOSE MODIFICATION GUIDELINES IN THE PROTOCOL.
	Consistency Trial Treatment Profile	Is the clinical/pathological presentation of the AE consistent with previous knowledge regarding Merck product or drug class pharmacology or with toxicology ?
The assessment of relationship will be reported on the case report forms /worksheets by an investigator who is a qualified physician according to his/her best clinical judgment, including consideration of the above elements.		
Record one of the following	Use the following scale of criteria as guidance (not all criteria must be)	present to be indicative of Merck product relationship).
Yes, there is a reasonable of possibility of Merck product relationship.	There is evidence of exposure to Merck product. The temporal sequence The AE is more likely explained by Merck product than by another cause	the AE onset relative to the administration of Merck product is reasonable.
No, there is not a reasonable possibility of Merck product product. relationship	Subject did not receive the Merck product OR temporal sequence of the the AE is more likely explained by another cause than the Merck	AE onset relative to administration of Merck product is not reasonable OR (Also entered for a subject with overdose without an associated AE.)

#### 6.4.9 Principal Investigator Responsibility for Reporting Adverse Events

All Adverse Events will be reported to regulatory authorities, IRB/IECs and investigators in accordance with all applicable global laws and regulations.

### 7.0 STATISTICAL ANALYSIS PLAN

#### 7.1 Statistical Analysis Plan Summary

Forty evaluable subjects will be enrolled in the study. Two sequential run-in cohorts will be conducted to confirm safety, after which the remaining patients will be randomized between preoperative pembrolizumab versus preoperative pembrolizumab and SRT. The primary study endpoint is based on the anticipated degree of improvement in tumor immunogenicity as measured by the number of infiltrating CD3+ T cells/  $\mu\text{m}^2$  in the lung cancer tissue.

#### 7.2 Statistical Analysis Plan

Sample size justification:

The sample size is based upon the anticipated number of patients who will have samples that will be useful for study of immunologic changes in the number of infiltrating CD3+ T cells/ $\mu\text{m}^2$  in the lung cancer tissue between the pre-treatment (baseline) biopsy and post-treatment thoracotomy specimens.

The sample size is fixed at 40 patients. It assumes successful accrual of 6 patients from each of the two run-in cohorts and an additional 28 patients from the randomized expansion cohort, for a total of 40 patients. However, past clinical experience indicates that as many as one-third of patients may not be able to complete a new successful core needle biopsy procedure and only prior archived tissues will be available for any analysis (which may eventually turn out to be insufficient to evaluate for primary endpoint). These patients who enrolled but whose core biopsy is later found to be inadequate after initiation of therapy will be allowed to continue on the protocol but will not be included in the primary endpoint.

The null hypothesis is that a two-fold increase will be seen in 15% of the evaluable 26 patients (assuming up to one third of samples may be unevaluable for primary endpoint). The alternative hypothesis is that a two-fold increase will be seen in 40% of the evaluable 26 patients. This yields 90% statistical power, with one sided 5% alpha level based on an exact binomial test.

The goal of achieving a two-fold increase in 40% of the evaluable population is a reasonable one, as estimated from a previous study showing greater-than-three-fold increase in 57% of patients when CD3+ T cells/ $\mu\text{m}^2$  were measured in prostate cancer tissue treated with a cell- based cancer immunotherapy, with a null hypothesis having been set at a two-fold increase in 15% of the population (Fong 2014). The current study includes immunotherapy +/- stereotactic radiation therapy, both of which are anticipated to create increased immunogenicity against NSCLC.

It is anticipated that accrual will be completed in 10 months (4 patients per month), with each patient treated for approximately 2.5-3 months and then followed for 12 months after completing protocol therapy. Total study duration is 25 months.

A binomial exact test will be performed to compare the proportion of patients achieving a two-fold increase from baseline using a 1-sided test under the null hypothesis of 15%. Exact 95% confidence intervals will be presented with associated estimate. P <0.05 will be considered statistically significant.

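### Minor, wrong as written: Section 7.2 states 90% power for 26 evaluable patients with an exact binomial test, but that test has 87.8% power at 26 and reaches 90.5% at 27

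*Combined protocol and SAP*

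**What the plan says.** Everything needed for the power calculation is in the sample size justification of Section 7.2.

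- **Enrolment:** "The sample size is fixed at 40 patients", made up of 6 + 6 in the run-in cohorts and 28 in the expansion cohort.
- **Expected loss:** past experience is that "as many as one-third of patients may not be able to complete a new successful core needle biopsy procedure". The plan carries this forward as "assuming up to one third of samples may be unevaluable for primary endpoint".
- **Null:** "The null hypothesis is that a two-fold increase will be seen in 15% of the evaluable 26 patients".
- **Alternative:** "The alternative hypothesis is that a two-fold increase will be seen in 40% of the evaluable 26 patients".
- **Power claim:** "This yields 90% statistical power, with one sided 5% alpha level based on an exact binomial test".

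The last paragraph of Section 7.2 names the same test for the analysis, a one-sided exact binomial test against 15%, and sets the decision rule: "P <0.05 will be considered statistically significant". No rejection cutoff (number of responders) is given.

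**The concern.** The responder count is a whole number, so an exact binomial test can rarely use its full 5%. Its power at a given sample size can fall below what a normal approximation suggests. The sentence gives sample size, both rates, alpha, sidedness and test, so it can be checked directly, and it does not reproduce.

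The planning count is also slightly off. Two thirds of 40 is 26.67, and the plan uses 26. That requires 14 of 40 patients to be lost, which is more than the one third assumed.

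This is the only power figure given for the primary endpoint, so it should be correct for the number and test beside it. The validity of the final test is not at stake.

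**Working it through.** **Inputs** (all from Section 7.2): n = 26 evaluable; p0 = 0.15; p1 = 0.40; one-sided exact binomial; reject if P < 0.05; 40 enrolled; at most one third unevaluable.

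**Formulas.** Let X be the number of patients with a two-fold increase. The cutoff r is the smallest integer with P(X ≥ r | n, 0.15) < 0.05. Attained alpha is P(X ≥ r | n, 0.15), and power is P(X ≥ r | n, 0.40).

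**Step 1: the plan's own figure, n = 26.**

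| Cutoff | P(X ≥ r given 0.15) | P(X ≥ r given 0.40) | 5% test? |
|---|---|---|---|
| 7 | 0.0833 | 0.9441 | no |
| 8 | 0.0321 | 0.8784 | yes |

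The cutoff is 8, attained alpha 3.2% and power 87.8%. The stated 90% is not reproduced. The shortfall is 90.0 − 87.8 = 2.2 points, and type II error is 100 − 87.8 = 12.2%.

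**Step 2: does another reading at n = 26 give 90%?**

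| Method | Power at n = 26 |
|---|---|
| Two-sided exact (cutoff 9) | 77.4% |
| One-sided mid-p (cutoff 8) | 87.8% |
| Normal approximation, null variance | 92.0% |
| Same, with continuity correction | 88.6% |
| Normal approximation, alternative variance | 83.1% |
| Arcsine approximation | 90.0% |

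For the arcsine approximation, h = 2·asin(√0.40) − 2·asin(√0.15) = 0.5740, and power = Φ(0.5740·√26 − 1.645) = 0.900. The stated 90% therefore agrees with an approximation and not with the exact test named. The plan does not say how the figure was obtained, so this is only a possible source.

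**Step 3: the loss assumption.** One third of 40 is 13.33.

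- 13 lost: 13/40 = 32.5%, leaving 27 evaluable.
- 14 lost: 14/40 = 35.0%, leaving 26 evaluable.

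Read literally, a loss of no more than one third leaves at least 27.

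**Step 4: power at n = 27.** P(X ≥ 7 | 0.15) = 0.0986 and P(X ≥ 8 | 0.15) = 0.0398, so the cutoff is again 8. Attained alpha is 4.0% and power P(X ≥ 8 | 0.40) = 0.9047, or 90.5%. This is the smallest n at which the exact test reaches 90%.

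**Step 5: larger evaluable counts.** Exact power does not rise steadily, because it drops each time the cutoff moves up by one.

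| n | 27 | 28 | 29 | 30 | 31 | 32 | 33 |
|---|---|---|---|---|---|---|---|
| Power (%) | 90.5 | 92.6 | 88.1 | 90.6 | 92.6 | 94.3 | 95.6 |

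| n | 34 | 35 | 36 | 37 | 38 | 39 | 40 |
|---|---|---|---|---|---|---|---|
| Power (%) | 92.7 | 94.2 | 95.5 | 96.5 | 97.3 | 95.5 | 96.5 |

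From 27 to 40 evaluable, only 29 falls below 90%.

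**The case against.** The best defence accepts the arithmetic and disputes its weight.

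*Rounding 26.67 down to 26 is ordinary caution, and one third is a rough figure.* This is fair as a reason to plan on 26. It does not make 90% the power at 26. If 26 is the deliberate conservative count, the power quoted should be the one that goes with it.

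*27 is not a guaranteed floor.* The endpoint needs a surgical specimen as well as a biopsy (Section 3.1). Some patients may become unresectable (Section 3.2, objective 7), and Section 5.9 does not replace those who leave before surgery with grade 3 or higher toxicity. Actual losses could exceed the biopsy failures. This stands as a caution. However, Section 7.2 sets the one-third limit on samples unevaluable for the primary endpoint, so 27 is what that assumption gives. If instead each of 40 patients is assumed independently evaluable with probability 2/3, exact power averaged over the evaluable count is 88.0%. That favours restating the power at 26.

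*The sample size was fixed by feasibility, and power is only reported.* This is partly right: the total of 40 is the sum of the cohort sizes. The sentence still offers the power as support for that number.

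*The gap comes only from discreteness.* This is true. A test randomized to use the full 5% would have 90.1% power at 26. The plan specifies no randomization at the boundary and rejects at P < 0.05, so the attainable figure remains 87.8%.

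**Conclusion.** The point holds, as a minor error. For 26 evaluable patients, 15% versus 40% and a one-sided exact binomial test at P < 0.05, power is 87.8% and not 90%, with attained alpha 3.2%. This rests only on the inputs in Section 7.2, and nothing elsewhere in the documents corrects it. The companion statement, that 27 evaluable patients give 90.5% at alpha 4.0%, is also correct. It assumes that the one-third limit covers every cause of an unevaluable primary endpoint.

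The practical effect is small. One more evaluable patient removes the shortfall, type I error is controlled below 5% either way, and the analysis and its interpretation do not change.

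**What to change.** Change the power sentence in Section 7.2 in one of two ways.

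1. **Keep 26 evaluable.** State that the exact one-sided test has 87.8% power with attained alpha 3.2%. This is the more conservative option and needs no further assumption.
2. **Plan on 27 evaluable** (40 enrolled, at most 13 unevaluable for any reason). State exact power 90.5% with attained alpha 4.0%. If this is chosen, change 26 to 27 in the null and alternative statements too, and note that power is 88.1% if exactly 29 are evaluable.

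In either case it helps to add the rejection rule, 8 or more responders at that count, so that a reader can reproduce the figure.

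The cost is a small wording change in the SAP. The stated power falls by 2.2 points under option 1 and stays at about 90% under option 2. Enrolment, test, decision rule and conduct do not change.

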### 3.0 OBJECTIVES & HYPOTHESES

#### 3.1 Primary Objectives & Hypotheses

(1) **Objective:** To determine the change in the number of infiltrating CD3+ T cells/  $\mu\text{m}^2$  in the lung cancer tissue between the paired biopsy and thoracotomy specimens, as quantified by immunohistochemistry (IHC) and image analysis.

**Hypothesis:** For resectable NSCLC, the administration of pembrolizumab +/- low-dose stereotactic SRT in the preoperative window will enhance tumor immunogenicity, resulting in two-fold greater infiltrating CD3+ T cells/  $\mu\text{m}^2$  in the primary and/or regional environment at the time of surgical resection, as compared to the time of initial biopsy.

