#### 4.3.4 Rationale for Endpoints

The primary endpoint for this study is the change in number of infiltrating CD3+ T cells/  $\mu\text{m}^2$  in the lung cancer tissue from before and after pembrolizumab +/- SRT, based on quantification using immunohistochemistry (IHC) and image analysis. This endpoint was selected as a marker of T cell proliferation and activation. It is expected that immunologic activation would be reflected by the presence of this biomarker. The purpose of this study is to determine whether neoadjuvant pembrolizumab +/- SRT is sufficient to produce a two-fold change in the CD3+ T cell population, comparing pre-treatment biopsy tissue to post-treatment resection specimens.

Despite the generally high efficacy of surgery in producing local control for most NSCLC patients, a large percentage will succumb to regional or distant metastatic disease manifestation. Therefore, this study will also include exploratory objectives aimed at the possibility of a potential improvement in 1-year clinical outcomes from the addition of neoadjuvant immune modulation.

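### The primary objective is the change in CD3+ density and the hypothesis a two-fold rise, but the only planned analysis tests whether more than 15% of patients double, so the change is never estimated and a success near the boundary does not show a two-fold rise

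*Combined protocol and SAP*

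**What the plan says.** - **Objective (3.1).** "To determine the change in the number of infiltrating CD3+ T cells" per unit area between the paired biopsy and thoracotomy specimens.
- **Hypothesis (3.1).** Preoperative treatment "will enhance tumor immunogenicity, resulting in two-fold greater infiltrating CD3+ T cells" at resection compared with biopsy.
- **Endpoint rationale (4.3.4).** The study asks whether treatment "is sufficient to produce a two-fold change in the CD3+ T cell population".
- **Sample size (7.2).** "The null hypothesis is that a two-fold increase will be seen in 15% of the evaluable 26 patients"; "The alternative hypothesis is that a two-fold increase will be seen in 40% of the evaluable 26 patients". The stated power is 90% at one-sided 5%, by exact binomial test.
- **Analysis (7.2).** "A binomial exact test will be performed to compare the proportion of patients achieving a two-fold increase from baseline using a 1-sided test", under the 15% null, with an exact 95% confidence interval for the estimate and significance at p < 0.05.
- **Basis for the rates (7.2).** The 40% target is argued from an earlier prostate cancer study, "with a null hypothesis having been set at a two-fold increase in 15% of the population".
- **Tissue (6.2.5.1, 6.2.5.2, 5.1.1).** Baseline is one to four cores, with fine-needle aspirate or archived tissue accepted in some cases. Post-treatment tissue is an excisional sample from the medial part of the tumour.

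No estimate, interval or test of the fold change itself is planned. The documents give no SD, repeatability figure or untreated doubling rate for CD3+ density.

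**The concern.** The objective and hypothesis concern the size of the change in infiltration. The analysis reduces each pair of specimens to doubled or not doubled and asks whether doublers exceed 15%. A modest rise in most patients and a large rise in a minority could give the same count, and the planned output would not tell them apart.

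At stake is what a positive result may be said to show. Section 7.2 does not state the claim that success permits, and sections 3.1 and 4.3.4 supply a larger one than the test can carry. The trial is open label, so a fold-change summary chosen after the data are seen would be open to doubt.

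**Working it through.** **Inputs from section 7.2.** n = 26 evaluable, null 15%, alternative 40%, one-sided 5%, exact binomial. **Assumed:** log-normal post/pre ratios with natural-log SD s from 0.5 to 1.0.

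**1. The plan's own figure.** Find the smallest r with P(X ≥ r | 26, 0.15) ≤ 0.05.
- r = 7: size 8.3%, too large.
- r = 8: size 3.2%; power P(X ≥ 8 | 26, 0.40) = 87.8%.

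The stated 90% is a near miss. With n = 27 (40 × 2/3 = 26.7, rounded up) and r = 8, power is 90.5%. This is a small separate matter.

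**2. What success requires, with no distribution assumed.**
- The boundary is 8/26 = 30.8% doubling, so 26 − 8 = 18 patients have not doubled. The 13th and 14th ordered ratios are then both below 2, and so is the sample median.
- Under the alternative, P(ratio ≥ 2) = 0.40 < 0.50, so the true median is below 2 in the situation the trial is powered to detect.
- A sample median of at least 2 is assured once 14 of 26 double. Under the alternative, P(X ≥ 14 | 26, 0.40) = 10.8%, against 87.8% for passing the test.

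**3. How far below two-fold, under the log-normal assumption.** If a share p of patients double, median = exp(ln 2 − z(1−p) × s), with ln 2 = 0.693, z = 0.502 at p = 8/26 and z = 0.253 at p = 0.40. For example, at 8/26 and s = 0.5: exp(0.693 − 0.251) = 1.56; at s = 1.0: exp(0.693 − 0.502) = 1.21.

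**4. If success were read as a treatment effect on CD3+.** With no true change, P(doubling) = q = 1 − Φ(0.693/s), and the chance of success is P(X ≥ 8 | 26, q).

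| s | Median at 8/26 | Median at 40% | q, no change | P(success), no change |
|---|---|---|---|---|
| 0.5 | 1.56 | 1.76 | 8.3% | 0.09% |
| 0.67 | 1.43 | 1.69 | 15.0% | 3.3% |
| 0.8 | 1.34 | 1.63 | 19.3% | 11.2% |
| 1.0 | 1.21 | 1.55 | 24.4% | 29.0% |

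The 15% null coincides with no change only at s of about 0.67 (0.693/1.036). The 3.3% in that row differs from 3.2% only because s is rounded.

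**5. Power of a paired analysis.** A one-sided 5% paired t-test on log ratios at 40% doubling has non-centrality (0.693 − 0.253s)/s × √26. This is 3.98 at s = 0.67 (power 98.7%) and 2.24 at s = 1.0 (power 70.4%). The exact test has 87.8% in both cases.

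**The case against.** The strongest reply is that a responder endpoint at the two-fold threshold is a legitimate way to make the hypothesis operational. Section 7.2 states null and alternative as proportions, and section 3.1 says neither mean nor median. That stands: this is a gap between hypothesis and test, not a contradiction. It leaves the change unestimated, and it does not make a boundary success evidence of a two-fold rise.

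A reader might infer more than the documents support:

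- **That the size of the test depends on sampling noise.** Against the stated null, size is 3.2% whatever the noise. The last column of the table applies only if the null is replaced by no change, which the plan does not test.
- **That no positive result supports the hypothesis.** If 14 or more of 26 double, the sample median is at least two-fold. The weakness lies nearer the boundary.
- **That a paired test is generally more powerful.** It is at SD 0.67 and is not at SD 1.0. The documents do not say which applies.
- **That the 15% was simply borrowed.** The sentence in 7.2 can be read as describing either the earlier study or this one. Either way, the documents do not present 15% as a repeat-sampling rate for core against excisional tissue.
- **That a two-fold claim should require the lower confidence limit of the ratio to reach 2.** The plan sets no such criterion. Under the log-normal model it would be met with a probability of only about 0.07% at the 40% alternative.

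**Conclusion.** The point holds as a mismatch between the stated primary question and the single planned analysis. That 18 of 26 patients may fail to double in a successful trial, and that the design alternative implies a median rise below two-fold, follow from the plan's own figures without a distributional assumption. The medians of 1.56 to 1.21 at the boundary, and the 0.09% to 29% chance of success with no change, rest on log-normal ratios and an assumed SD of 0.5 to 1.0. They show how widely the interpretation can vary and are not estimates for this trial.

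The exact test needs no replacement. What is missing is an estimate of the change and a stated limit on the claim. The amendment should be made: it is cheap, and without it the stated objective goes unanswered.

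**What to change.** 1. In 7.2, keep the one-sided exact binomial test as the primary analysis.
2. Beside it, pre-specify the geometric mean (or median) post/pre ratio of CD3+ density in the evaluable patients, with a two-sided 95% confidence interval. Add a supportive paired analysis of log ratios or a Wilcoxon signed-rank test, and state the offset used for zero counts.
3. State in 7.2 that success on the primary test means that more than 15% of patients had at least a two-fold increase, and nothing further about the average or typical rise.
4. Reword the hypothesis in 3.1 and the purpose in 4.3.4 to match.

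The cost is a text amendment: same patients, specimens and sample size. The permitted claim becomes less favourable. The added ratio would not remove any systematic difference between core and excisional tissue, which would bias it as it would the responder count, so that limitation should be reported with it.
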